6.6.2.1 Dose Modifications for Overlapping Toxicities

Participants may have chemotherapy discontinued and continue on blinded study intervention. Similarly, participants may discontinue blinded study intervention and continue on chemotherapy alone during the first 4 cycles, if appropriate.

Reduction of 1 chemotherapy agent and not the other agent is appropriate if, in the opinion of the investigator, the toxicity is clearly related to one of the treatments. If, in the opinion of the investigator, the toxicity is related to the combination of both chemotherapy agents, both drugs should be reduced, interrupted, or discontinued according to recommended dose modifications. Chemotherapy may be interrupted for a maximum of 6 weeks from the last

dose if due to an AE. If the toxicity is related to the combination of etoposide/platinum chemotherapy and blinded study intervention, all 3 agents should be reduced (if applicable), interrupted, or discontinued according to the recommended dose modifications.

6.6.2.2 Other Allowed Dose Interruptions With Chemotherapeutic Agents

These serve as a guide and do not replace investigator judgment and applicable local label recommendations, if more stringent. During Cycles 1 through 4 of blinded study intervention and etoposide/platinum:

- If etoposide dosing is delayed or interrupted, the platinum agent and the blinded study intervention should also be delayed/interrupted. If etoposide/platinum is delayed or interrupted during Cycles 1 through 4, participants should be seen weekly until toxicity resolves.
- If cisplatin/carboplatin dosing is delayed or interrupted, etoposide, and blinded study intervention should also be delayed/interrupted. If etoposide/platinum is delayed or interrupted during Cycles 1 through 4, participants should be seen weekly until toxicity resolves.
- If blinded study intervention is delayed or interrupted, etoposide/platinum therapy can continue as scheduled. Blinded study intervention administration should be attempted at the next cycle of therapy.
- Each chemotherapy cycle may not be delayed by more than 3 weeks (>21 consecutive days) despite supportive treatment (ie, chemotherapy may be interrupted for a maximum of 6 weeks from last dose). If only one of the agents is thought to be causing the specified toxicity leading to a 21-day delay of administration of the next cycle, that chemotherapeutic agent can be stopped and treatment can continue with blinded study intervention, with or without the remaining chemotherapy drug.
- Etoposide/platinum administration may be interrupted for situations other than treatment-related AEs such as medical or surgical events and/or unforeseen circumstances not related to study intervention. However, study intervention is to be restarted within 3 weeks, 21 days, of the originally scheduled dose and within 42 days of the previously administered dose, unless otherwise discussed with the Sponsor. The reason for study intervention interruption is to be documented in the participant's study record.

6.7 Intervention After the End of the Study

There is no study-specified intervention after the end of the study.

6.8 Clinical Supplies Disclosure

The emergency unblinding call center will use the intervention/randomization schedule for the study to unblind participants and to unmask study intervention identity. The emergency

unblinding call center should only be used in cases of emergency (see Section 8.1.10). If the emergency unblinding call center is not available for a given site in this study, the central electronic intervention randomization system (IRT) should be used to unblind participants and to unmask study intervention identity. The Sponsor will not provide random code/disclosure envelopes or lists with the clinical supplies.

6.9 Standard Policies

Not applicable.

08RNJZ

7 DISCONTINUATION OF STUDY INTERVENTION AND PARTICIPANT WITHDRAWAL

At implementation of Amendment 05, the below changes apply. The changes listed below supersede any protocol content/instructions from previous amendments.

- Participants with access to approved SOC (eg, immunotherapy, chemotherapy, targeted therapy) should be considered for discontinuation from the study. Those benefiting from atezolizumab, but unable to access it as SOC outside the study, may continue on study and receive treatment with atezolizumab until discontinuation criteria are met. The final required study visit will be the Safety Follow-up Visit.
- Participants who complete study treatment or otherwise meet EOT criteria will be discontinued from the study after the EOT visit and any required safety follow-up visit.
- There will be no follow up for survival status. Participants currently in imaging follow-up or survival follow-up are considered to have completed the study and therefore should obtain imaging and further oncological care as per local SOC. Standard safety reporting should, however, continue, as applicable.
- Participants remaining on study at the time of Amendment 05 should continue to be monitored in the study through the AE reporting period (Section 8.4).

Existing protocol content is retained for historical reference.

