Treatment Cycle:			1			2			3			4		5+	Discon	Protocol Amendment 04 implementation: Participants who continue atezolizumab under the study, safety assessments and safety related data collection including safety follow-up and laboratory assessments, should continue as per current protocol.
Day (in Cycle)		1	2&3	8	1	2&3	8	1	2&3	8	1	2&3	8	1	ЕОТ	
Scheduling Window (Days)	-28 to -1			±1	±3		±1	±3		±1	±3		±1	±3	(±3 days)	
EQ-5D-5L		x			х			Х			x			х	X	PROs will also be obtained at the EOT Visit. If EOT Visit occurs 30 days from the last dose of study intervention, at the time of the mandatory Safety Follow-up Visit, ePROs do not need to be repeated. ePROs should be administered in the following order: EORTC QLQ-C30, EORTC QLQ-LC13 and EQ-5D-5L.

AE=adverse event; aPTT=activated partial thromboplastin time; C=cycle; CR=complete response; CT=computed tomography; D=day; DBP=diastolic blood pressure; discon=discontinuation; ECG=electrocardiogram; EORTC=European Organization for the Research and Treatment of Cancer; EOT=end-of-treatment; FBR=future biomedical research; FSH=follicle-stimulating hormone; HBV=hepatitis B virus; hCG=human chorionic hormone; HCV=hepatitis C virus; HIV=human immunodeficiency virus; ICF=informed consent form; MRI=magnetic resonance imaging; PD=pharmacodynamic(s); PET=positron emission tomography; PK=pharmacokinetic(s); PRO=patient-reported outcome; PT=prothrombin time; PTT=partial thromboplastin time; Q3W=every 3 weeks; Q6W=every 6 weeks; Q9W=every 9 weeks; QLQ=quality of life questionnaire; RR=respiratory rate; SAE=serious adverse event; SBP=systolic blood pressure; SCLC=small cell lung cancer; SOP=standard operating procedure; TSH=thyroid-stimulating hormone; WOBCP=woman/women of childbearing potential.

Table 2Schedule of Assessments (Posttreatment Follow-up)

Protocol Amendment 04 implementation: Efficacy Follow-up and Survival Follow-up are no longer applicable. All participants on efficacy follow-up or survival follow-up are considered to have completed all study activities. Safety Follow-up will be the last visit for participants currently on treatment.

Study Period:		Posttreatment Follow-	ир	Notes
Treatment Cycle:	Safety Follow-up	Efficacy Follow-up	Survival Follow-up	
Day (in Cycle)	30 days from last dose (+7 days)	Per imaging schedule	Every 12 weeks (±7 days)	
Administrative Procedures				
Prior/Concomitant Medication Review	Х			
Posttreatment Anticancer Therapy Status	Х	Х	Х	

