Vital Status			Х	After verified disease progression or start of new anticancer treatment. In addition, upon Sponsor request, participants may be contacted for vital status at any time during the course of the study.
Tumor Scan				Scans should follow calendar days from randomization and should not be adjusted for dose delays or cycle starts. Unscheduled scans can be performed as clinically indicated. Scans must be submitted and reviewed by BICR. See Section 8.2 for full details.
CT/MRI of chest, abdomen, and pelvis		Х		Use the same imaging modality for all evaluations.
Bone Scan		Х		On-study bone scans should be acquired as clinically indicated or to confirm a CR when bone metastases were present at Screening.
Brain Scan		X		For participants without brain metastases at Screening, on- study brain scans are required at Q12W (84 days \pm 7 days) through Week 48 and then Q24W (168 days \pm 7 days) through Week 96 or more often as clinically indicated. For participants with brain metastases present at Screening, on-study brain scans are to be acquired at all scheduled post-baseline imaging timepoints, or more often as clinically indicated, and to confirm a CR.
Safety Procedures				
Directed Physical Examination	Х			
Vital Signs	Х	1	1	DBP, SBP, heart rate, RR, temperature, pulse oximetry

Study Period:		Posttreatment Follow-	սթ	Notes
Treatment Cycle:	Safety Follow-up	Efficacy Follow-up	Survival Follow-up	
Day (in Cycle)	30 days from last dose (+7 days)	Per imaging schedule	Every 12 weeks (±7 days)	
Audiometry	Х			To be performed if this is the local standard of care only when cisplatin is chosen as the platinum agent. May be performed more often as clinically indicated.
ECOG Performance Status	X			
Thyroid Function Tests (TSH, T3, free T4)	Х			
Hematology	Х			
Chemistry	Х			
AE/SAE review	Х			Record all AEs occurring within 30 days after last dose of study intervention. Record all SAEs occurring up to 90 days after last dose of study intervention or 30 days after last dose of study intervention if the participant initiates new anticancer therapy, whichever comes first. Any treatment-related SAEs must be reported regardless of time they occur.
Patient-Reported Outcomes				As of Amendment 04, PROs will no longer be collected on any participants.
EORTC QLQ-C30	X			
EORTC QLQ-LC13	X			
EQ-5D-5L	X			

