- All AEs meeting serious criteria, from the time of intervention randomization through 90 days after cessation of study intervention or 30 days after cessation of study intervention if the participant initiates new anticancer therapy, whichever is earlier, must be reported by the investigator.
- All pregnancies and exposure during breastfeeding, from the time of intervention randomization through the time required to eliminate systemic exposure after cessation of study intervention as described in Sections 5.1 and 8.3.6, or 30 days after cessation of study intervention if the participant initiates new anticancer therapy must be reported by the investigator.

• Additionally, any SAE brought to the attention of an investigator at any time outside the time specified above must be reported immediately to the Sponsor if the event is considered related to study intervention.

Investigators are not obligated to actively seek AEs or SAEs or other reportable safety events in former study participants. However, if the investigator learns of any SAE, including a death, at any time after a participant has been discharged from the study, and the investigator considers the event to be reasonably related to the study intervention or study participation, the investigator must promptly notify the Sponsor.

All initial and follow-up AEs, SAEs, and other reportable safety events will be recorded and reported to the Sponsor or designee within the time frames as indicated in Table 10.

Exception: A positive pregnancy test at the time of initial screening is not a reportable event unless the participant has received study intervention.

Type of Event	Reporting Period: Consent to Randomization/ Allocation	Reporting Period: Randomization/ Allocation Through Protocol- specified Follow- up Period	Reporting Period: After the Protocol- specified Follow- up Period	Time Frame to Report Event and Follow-up Information to Sponsor
NSAE	Report if: - due to protocol- specified intervention - causes exclusion - participant is receiving placebo run-in or other run- in treatment	Report all	Not required	Per data entry guidelines
SAE including Cancer and Overdose	Report if: - due to protocol- specified intervention - causes exclusion - participant is receiving placebo run-in or other run- in treatment	Report all	Report if: – drug/vaccine related. (Follow ongoing to outcome)	Within 24 hours of learning of event

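### Does the Amendment 05 text leave it unclear whether safety reporting ends at the Safety Follow-up Visit or runs on to day 90?

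*Combined protocol and SAP*

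**What the plan says.** The Amendment 05 list appears in Sections 1, 4, 6, 7, 8 and 9. Four of its statements matter here.

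- First bullet: "The final required study visit will be the Safety Follow-up Visit".
- Second bullet: participants who complete treatment or meet end-of-treatment criteria "will be discontinued from the study after the EOT visit and any required safety follow-up visit".
- Third bullet, after ending survival follow-up: "Standard safety reporting should, however, continue, as applicable".
- Fourth bullet: "Participants remaining on study at the time of Amendment 05 should continue to be monitored in the study through the AE reporting period", with a cross-reference to Section 8.4.

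Section 8.4.1 requires all adverse events to be reported for 30 days after study intervention stops. Serious events are reported "from the time of intervention randomization through 90 days after cessation of study intervention or 30 days after cessation of study intervention" if new anticancer therapy begins, whichever is earlier. The adverse event row of Table 2 carries the same rule: "Record all SAEs occurring up to 90 days after last dose of study intervention". Serious events judged related are reportable at any time. Section 8.4.1 adds: "Investigators are not obligated to actively seek AEs or SAEs or other reportable safety events in former study participants".

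The Table 1 note and Section 4.1 stop collection of posttreatment anticancer therapy status from Amendment 04. Table 2 still marks that item at the Safety Follow-up Visit.

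**The concern.** One bullet takes the participant out of the study at about day 30 to 37. Another keeps the same participant in the study through a period that, for serious events, can last to day 90. Both belong to Amendment 05, so the clause by which it overrides earlier amendments cannot rank them. The label matters because the duty to look actively for events lapses once someone is a former participant. Two sites could read the list differently, one continuing to ask about serious events and the other waiting to be told.

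The therapy item adds to the unease. The start of new anticancer therapy decides between a 30-day and a 90-day window, yet its collection is stopped in two places and still marked in a third.

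At stake would be incomplete capture of serious events with onset after the last visit, mainly those judged unrelated. Section 9.6.2 gives between-group intervals for serious events that reach 1% in a treatment group, so under-capture could in principle reach a reported table. Overall survival and progression-free survival are not involved.

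**Working it through.** This is mainly a matter of reading the passages side by side. The only arithmetic is on day counts.

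**Days without a scheduled visit.** Inputs: the Safety Follow-up Visit at day 30 with a window of +7 days (Table 2), and a 90-day limit for serious events (Section 8.4.1).

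- Visit on day 30: 90 − 30 = 60 days, and 60/90 = 67% of the window.
- Visit on day 37: 90 − 37 = 53 days, and 53/90 = 59%.
- Non-serious events with the visit at day 30 or later: no gap, because their window is 30 days.

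The 53 to 60 days apply only to participants whose window is 90 days. They count days without a visit, not events missed.

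**Did the amendments create the gap?** Table 2 marks adverse event review under Safety Follow-up only. It is not marked under Efficacy or Survival Follow-up. For a participant going straight to survival follow-up, Section 8.11.4.3 set the first contact 12 weeks (84 days) after the later of the discontinuation and safety visits. That is day 30 + 84 = 114 to day 37 + 84 = 121, or day 107 to 128 with the ±7-day window, already past day 90. Participants in efficacy follow-up had imaging visits that could fall inside the window, but without an adverse event mark. The absence of a scheduled serious-event review after the safety visit is therefore original design.

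**Does the duty depend on which bullet governs?** Section 8.4.1 defines the serious-event window by time since study intervention stopped. It does not make the duty depend on whether the participant is still in the study. Table 10 likewise asks for all serious events through the protocol-specified follow-up period. The duty to report a known serious event is the same under either bullet. Only active seeking differs.

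**Does the missing therapy date matter?**

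- Starts by about day 30: Section 6.5 records concomitant medication to day 30, and Section 8.1.6.2 to the Safety Follow-up Visit. Section 8.11.4.1 brings that visit forward when new therapy is about to begin.
- Starts after day 30: on a forward reading these cannot shorten the window, because the 30-day limit has already passed. They matter only if a later start closes the window retroactively, which Section 8.4.1 does not say.
- The mark in Table 2: the questionnaire rows of that table are also still marked, beneath a note that those data are no longer collected. The therapy mark looks like the same kind of residue, without its note.

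**The case for a change.** The strongest reply is that the second bullet speaks of leaving the study, not of ending visits, so the joint reading has to be supplied by the reader. The phrase used for the reporting period in the fourth bullet is undefined, and Section 8.4 holds several windows. A site that takes the second bullet at its word may stop asking about serious events at about day 37. Section 8.10 also wants hospitalizations and emergency visits over the same 90 days, again with no contact scheduled. A clarification letter and one telephone call per remaining participant would cost little.

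Part of this stands. The wording is untidy, and whether investigators should actively seek serious events between the last visit and day 90 is not stated. The rest does not carry far. The third bullet says safety reporting continues, which supports separating visits from reporting. The call would be a new procedure that the schedule never contained, and it would work against the amendment's stated aim of making the safety visit the last one. A sponsor could reasonably decline it. The documents give no number of remaining participants, no serious-event rate and no capture rate, so no gain from the call can be shown.

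**Conclusion.** The concern does not call for a change to the plan. The tension between the second and fourth bullets is real as wording, but they fit together if visits end at Safety Follow-up and Section 8.4.1 reporting continues for its own term. The leftover therapy mark in Table 2 is a clerical slip against an explicit instruction elsewhere. A line on both points could go into any later correspondence with sites, but no analysis waits on it.

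The possible effect is confined to serious events judged unrelated, with onset after the last visit, in participants with a 90-day window. Related events remain reportable without a time limit. The affected analysis is the end-of-study safety summary, which under Section 9.6.2 expects no Tier 1 tests and treats its intervals as descriptive. The experimental arm has been discontinued and no further efficacy analysis is planned.

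This rests on two assumptions: that sites read Section 8.4.1 as binding by days since study intervention stopped, and that a therapy start after day 30 does not close the window retroactively. If the second fails, some late events would be of uncertain eligibility for the window, but the duty to report known serious events inside it would not change.

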7.1 Discontinuation of Study Intervention

Discontinuation of study intervention does not represent withdrawal from the study.

As certain data on clinical events beyond study intervention discontinuation may be important to the study, they must be collected through the participant's last scheduled followup, even if the participant has discontinued study intervention. Therefore, all participants who discontinue study intervention before completion of the protocol-specified treatment period will still continue to be monitored in this study and participate in the study visits and procedures as specified in Section 1.3 and Section 8.11.3 unless the participant has withdrawn from the study Section 7.2.

Protocol Amendment 04 implementation: Per eDMC recommendation, there will be no collection of efficacy data, and the final visit in the study will be the safety follow-up visit. Participants who discontinue study intervention and have completed safety follow up will be considered to have completed the study.

Participants may discontinue study intervention at any time for any reason or be discontinued from the study intervention at the discretion of the investigator should any untoward effect occur. In addition, a participant may be discontinued from study intervention by the investigator or the Sponsor if study intervention is inappropriate, the study plan is violated, or for administrative and/or other safety reasons.

08RNIZ

22-JAN-2025

A participant must be discontinued from study intervention, but continue to be monitored in the study for any of the following reasons:

- The participant or participant's legally acceptable representative requests to discontinue study intervention.
- Any prolonged interruption of study intervention beyond the permitted periods, for irAE management or other allowed dose interruptions, as noted in Section 6.6.1, require Sponsor consultation prior to restarting treatment. If treatment will not be restarted, the participant will continue to be monitored in the study and the reason for discontinuation of study intervention will be recorded in the medical record.
- The participant has a medical condition or personal circumstance which, in the opinion of the investigator and/or Sponsor, placed the participant at unnecessary risk from continued administration of study intervention.
- The participant has a confirmed positive serum pregnancy test.
- Radiographic disease progression outlined in Section 8.2.1.4 (after obtaining informed consent addendum and Sponsor communication, the investigator may elect to continue treatment beyond investigator assessed disease progression).
- Any progression or recurrence of malignancy, or any occurrence of another malignancy that requires active treatment.
- Any study intervention-related toxicity specified as a reason for permanent discontinuation as defined in the guidelines for dose modification due to AEs in Section 6.6.
- Interruption of platinum-based chemotherapy for more than 6 weeks from the last dose without Sponsor consultation.
- Intercurrent illness other than another malignancy as noted above that prevents further administration of treatment.
- Use of prohibited medications or vaccinations as described in Section 6.5.
- The participant interrupts blinded study intervention administration for more than 12 consecutive weeks from last dose for an AE/toxicity or for more than 6 weeks from last dose for administrative reasons without Sponsor consultation.

For participants who are discontinued from study intervention, but continue to be monitored in the study, all visits and procedures, as outlined in the SoA, should be completed.

Discontinuation from study intervention is "permanent." Once a participant is discontinued from study intervention, they shall not be allowed to restart study intervention.

